### STUDY SUMMARY

**TITLE** Taperloc Microplasty vs. Taperloc Standard: Randomized Controlled Study on Bone Mineral Density

**DESIGN** Multi-Center Comparative Two Armed Randomized Controlled Study (Centralized Randomization run by Sponsor)

**PURPOSE** The primary purpose of this study is to measure the postoperative changes in bone mineral density, comparing the Taperloc Complete Reduced Distal Microplasty stem and the standard length Taperloc Complete Reduced Distal stem.

**OUTCOME MEASURES** The primary outcome measures are the change in bone mineral density in the Gruen zones surrounding the stem measured by DEXA and incidence of thigh pain.

The secondary outcome measures are the assessment of leg length and femoral offset, to determine the suitability of the implant size range and neck geometry, standard clinical scores (i.e. modified Harris Hip Score), complications, and survivorship analysis.

**POPULATION** 100 Patients:

50 with Taperloc Complete Reduced Distal stem.

50 with Taperloc Complete Reduced Distal Microplasty stem

Up to four sites will be used to enroll patients into this study

**ELIGIBILITY** To be included in the study, a patient must be prescribed a primary total hip

arthroplasty with the Taperloc system. The Taperloc system is to be used in accordance to the indications for use and contraindications detailed in the

approved labeling of the device.

**DURATION** 1 year recruitment, and 5 years follow up

**STUDY SPONSOR** Zimmer Biomet

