#### 2. STUDY DESIGN

#### 2.1. OVERALL DESIGN

This study is a multi centre, prospective two-way randomized comparative study, involving 100 patients, recruited among up to 2 centers (approximately 50 patients from each site). Patients will be randomized at the time of surgery into two groups, as detailed below.

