### 2.3. NUMBER OF SITES AND SUBJECTS/PROCEDURES

The total sample size is 100 hips in 100 patients recruited from up to two sites.

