#### **Exploratory Analyses**

Exploratory Analyses described below will be carried out if possible, depending on the data. If empty cells exist or models do not converge, these analyses will not be performed.

Repeated measures ANOVA models will be developed for each of the Gruen Zones to determine the effect of visit (time), treatment and baseline value of BMD on the BMD results. Baseline factors may also be included. To determine whether a factor has an effect on the BMD results, a Type 3 analysis of effects based on the F test will be conducted. Hypothesis testing will use  $\alpha$  = 0.05.

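### Site has no stated role in the randomisation or the analysis, and the protocol gives conflicting numbers of sites (up to four or up to two)

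*Combined protocol and SAP*

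**What the plan says.** **Randomisation.** The Study Summary gives the design as "Multi-Center Comparative Two Armed Randomized Controlled Study (Centralized Randomization run by Sponsor". Section 2.1 adds the timing: "Patients will be randomized at the time of surgery into two groups, as detailed below". No stratification factor, block size or method of generating the sequence is given anywhere. The Summary's population targets are "50 with Taperloc Complete Reduced Distal stem" and "50 with Taperloc Complete Reduced Distal Microplasty stem", so the intended split is 1:1 overall.

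**Number of sites.** The Summary states: "Up to four sites will be used to enroll patients into this study". Section 2.1 has patients "recruited among up to 2 centers (approximately 50 patients from each site". Section 2.3 agrees with Section 2.1: "The total sample size is 100 hips in 100 patients recruited from up to two sites". All three are current text.

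**Analysis.** Section 6.2 never mentions site. For continuous measures it offers a t-test, a Wilcoxon test or a one-way ANOVA as examples, all without adjustment. For categorical measures it names no test. The only model with covariates is the repeated measures ANOVA of BMD by Gruen zone. It is exploratory and includes visit, treatment and baseline BMD. It also allows that "Baseline factors may also be included", without saying which.

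**The concern.** Surgeon, DEXA scanner and patient mix can all change with site, so both primary endpoints (BMD change and thigh pain) may differ between sites for reasons unrelated to the stem. With 100 patients, allocation that ignores site can leave the arms unevenly spread over sites, and an unadjusted comparison then carries part of the site difference into the arm difference. Even with balanced arms, leaving site out of the model keeps between-site variation in the error term.

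The conflict over the number of sites adds to this, because neither site strata nor a site term can be set up until that number is settled. If the analysis plan says nothing, the choice to adjust for site is also left until the data are known.

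**Working it through.** The plan gives no figure for site imbalance or site effects, so there is none to reproduce. Its one calculated figure, the sample size for thigh pain, does not enter this point.

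**Inputs from the documents.** 100 patients, 50 per arm (Study Summary); two sites of about 50 (Section 2.1); two-sided alpha 0.05; thigh pain 15% against 5% (Section 6.1).

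**Assumptions.** Allocation not stratified by site (the documents are silent); equal site sizes; between-site differences in outcome as shown below.

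**1. Chance imbalance, two sites of 50.** Let k be the number of Microplasty patients at one site.

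| Allocation | Distribution of k | SD of k | 28:22 or worse | 30:20 or worse |
|---|---|---|---|---|
| Arms fixed at 50:50 overall | Hypergeometric(100, 50, 50) | 2.51 | 32% | 7.1% |
| Simple randomisation | Binomial(50, 0.5) | 3.54 | 48% | 20% |

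The first row fits the Summary's target of 50 and 50 better. With four sites of 25 and arms fixed at 50:50, simulation of 200,000 trials gives a 46% chance that at least one site is 16:9 or worse. For comparison, permuted blocks of 4 within site (an assumed size) would hold the within-site difference to 2 patients.

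**2. Shift in the BMD arm difference.** The site's share is k/50 of the Microplasty arm and (50 − k)/50 of the control arm, so

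shift = (2k/50 − 1) × site difference.

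- At 30:20 the multiplier is 60/50 − 1 = 0.20.
- Its mean absolute value over the hypergeometric distribution is 0.079.

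| Assumed site difference in BMD change | Mean absolute shift | Shift at 30:20 |
|---|---|---|
| 0.25 SD | 0.02 SD | 0.05 SD |
| 0.5 SD | 0.04 SD | 0.10 SD |

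The standard error of the arm difference at 50 per arm is √(2/50) = 0.20 SD.

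**3. Shift in the thigh pain difference.** The same formula applies. At a 30:20 split, assumed site differences of 5, 10 and 20 percentage points shift the arm difference by 1, 2 and 4 points. At 28:22 (multiplier 0.12) the shifts are 0.6, 1.2 and 2.4 points. The planned difference is 15 − 5 = 10 points.

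**4. Precision gained by adjusting BMD for site.** With two equal sites, a difference of δ total SD explains δ²/4 of the variance. For δ = 0.5 this is 0.25/4 = 0.0625, about 6%.

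- Unadjusted: non-centrality 0.5 × √(50/2) = 2.50; power about 70%.
- Adjusted: 0.5/√(1 − 0.0625) = 0.516, and 0.516 × 5 = 2.58; power about 72%.
- For δ = 0.25, site explains 0.0625/4 = 1.6% of the variance and power stays at about 70%.

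**5. Events available for a stratified thigh pain comparison.** 50 × 0.15 + 50 × 0.05 = 7.5 + 2.5 = 10 expected events: about 5 per site with two equal sites, or 2.5 with four.

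**The case against.** - **Silence is not evidence of non-stratification.** A reader might infer that the sponsor runs a single list with no site stratum. The documents do not say so, and a central system can stratify. This objection stands, and every imbalance figure above is conditional on unstratified allocation.
- **Chance imbalance is not bias.** A reader might also infer that the arm comparison would be biased. Imbalance under randomisation is random in direction, and the error rate of the unadjusted test already allows for it. This stands too: what remains is chance confounding in the one trial that is run, and lost precision.
- **Larger effects can be produced by choosing larger inputs.** The 0.10 SD shift belongs to a 30:20 split, which is uncommon with arms fixed at 50:50. Power of 74% or 79% would need site to explain 10% or 20% of the variance; 20% implies a site difference of about 0.9 total SD. The documents give no site effect of any size, so they do not support those figures.
- **The plan offers partial cover.** BMD is analysed as change from the immediate post-operative scan, so a constant scanner offset cancels if the same scanner is used throughout. The exploratory model could admit site as a baseline factor. But change scores do not remove differences in surgery or patient mix, and the exploratory model is optional and is dropped if it fails to converge.
- **Strata for thigh pain would be sparse.** With about 10 expected events this is fair, particularly with four sites. It argues for a Mantel-Haenszel type comparison over a model with many site terms.

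**Conclusion.** The point holds as a cheap improvement. Three things can be read directly from the text: the number of sites conflicts, stratification by site is not specified, and Section 6.2 gives site no role. The statistical consequence is modest. It rests on unstratified allocation, equal sites and an assumed site difference. With a 0.5 SD site difference in BMD change, the typical shift is about a fifth of the standard error (0.04 against 0.20 SD), and adjustment gains about 2 points of power. If the sponsor already stratifies by site, the imbalance concern falls away, but an analysis that ignores site would then not reflect the design. The mismatch between two and four sites needs correcting either way; it does not itself show that allocation is unstratified.

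**What to change.** 1. Give the same number of sites in the Study Summary and Sections 2.1 and 2.3, with the expected number of patients per site.
2. State how the sequence is generated and whether it is stratified by site. If enrolment has not begun, stratify by site using permuted blocks of randomly varying size.
3. In Section 6.2, pre-specify site as a fixed effect in the BMD and hip-score models, and a site-stratified Mantel-Haenszel type comparison for thigh pain.

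**Cost.** A setting in a system the sponsor already runs, a short addition to Section 6.2 and a corrected figure. Statistically, one degree of freedom with two sites or three with four, and sparse thigh pain strata if four sites are used. If enrolment has begun, the allocation method should be reported as it was used; the analysis change and the corrected number of sites still apply.

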#### 1. INTRODUCTION

#### 1.1. BACKGROUND

The Taperloc Microplasty cementless stem is designed to transmit load to the proximal femur, thereby preserving bone density, and preventing long term instability and loosening secondary to proximal bone resorption. The primary aim of this study is therefore to compare the postoperative changes in bone density with the Taperloc Microplasty stem, using the standard length Taperloc stem as a control.

In addition, the Taperloc stem has historically had a neck angle of 138°. There have been criticisms that this neck angle is too high for the typical Korean population. The newer Taperloc Complete system (both Microplasty and standard length) has a neck angle of 133°. A secondary aim is occurrence ratio of thigh pain difference between Microplasty and standard stem in Korean population

#### 1.2. DEVICE DESIGN AND DESCRIPTION

The Taperloc stem is designed after the philosophy of a flat tapered wedge. It has evolved to incorporate the Reduced Distal and Microplasty stems to better address all patient anatomies, and facilitate multiple surgical techniques.

The Flat Tapered Wedge Geometry enhances proximal loading, preserves bone, and provides rotational stability. Standard and lateralized options reproduce various patient anatomies without lengthening the leg

The stem is manufactured from Titanium Alloy Ti-6AL-4V, which allows for stress transfer to preserve cortical density. Titanium alloy porous plasma spray coating allows for initial scratch-fit stability and bone fixation. The Reduced Distal Stem Option allows the stem to be used in femoral canals with proximal/distal mismatch

The Microplasty Stem has a stem length reduced by 35 mm. This accommodates a minimally invasive approach, preserves soft tissues and bony structures, and ensures proximal stress transfer.

Product codes for the stems to be used in this study are listed below:

Full Length, Reduced Distal				
Size	Standard Offset	High Offset		
5x130	51-100050	51-101050		
6x132	51-100060	51-101060		
7x134	51-100070	51-101070		
8x136	51-100080 51-1010			
9x137	51-103090	51-104090		
10x140	51-103100	51-104100		
11x142	51-103110	51-104110		
12x144	51-103120	51-104120		
13x146	51-103130	51-104130		
14x148	51-103140	51-104140		
15x150	51-103150	51-104150		
16x152	51-103160	51-104160		
17x154	51-103170 51-1041			
18x156	51-103180 51-10418			
20x160	51-103200 51-10420			
22x164	51-103220	51-104220		
24x167	51-103240	51-104240		

Microplasty				
Size	Standard Offset	High Offset		
5x95	51-108050	51-109050		
6x97.5	51-108060	51-109060		
7x99	51-108070	51-109070		
8x101	51-108080	51-109080		
9x102.5	51-106090	51-107090		
10x105	51-106100	51-107100		
11x107.5	51-106110	51-107110		
12x109	51-106120	51-107120		
13x111	51-106130	51-107130		
14x113	51-106140	51-107140		
15x115	51-106150	51-107150		
16x117	51-106160	51-107160		
17x119	51-106170	51-107170		
18x121	51-106180	51-107180		
20x125	51-106200	51-107200		
22x129	51-106220	51-107220		
24x132	51-106240	51-107240		

### 1.3. RATIONALE FOR CURRENT STUDY

Stress shielding in cementless hip replacement leads to bone resorption. Not only does that increase the likelihood of long term aseptic loosening, but the reduction in bone stock could compromise the outcome of revision surgery. This is particularly important considering that cementless components are frequently used preferentially in young patients. Not only is the revision risk for a given implantation time higher with young patients, but life expectancy is higher as well. This means that young patients are much more likely to need revision surgery in their lifetime. Preservation of bone stock in order to keep revision options open is therefore a very important consideration.

One way to preserve the bone stock and to reduce stress-shielding bone resorption of the proximal femur is by removing the distal stem of the femoral component and providing metaphyseal fixation. Alternatively, reducing the size of the distal stem could also encourage metaphyseal fixation. The questions arise which is most effective at encouraging proximal load

transfer, and whether it is possible to obtain strong and long-lasting fixation of the femoral component without diaphyseal anchoring.

The rationale for this study is therefore to determine whether radiographic results and stress shielding are similar between the short and conventional length cementless femoral components with identical metaphyseal design.

#### 1.4. STUDY PURPOSES

The main objectives of the study are to:

- Compare the postoperative changes in bone density with the Taperloc Microplasty stem, using the standard length Taperloc stem as a control.
- Compare and confirm the stability and fixation of short and standard Taperloc hip implants.
- Compare clinical scores in patients receiving the short and standard Taperloc stems.
- Collect survivorship data
- Determine whether the geometry and options available with the Taperloc Complete hip system can accurately reconstruct leg length and offset in this patient population.

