#### 2.2. STUDY GROUPS/TREATMENTS

The first group will receive a Taperloc Complete Reduced Distal standard length stem, and the second group will receive a Taperloc Complete Reduced Distal Microplasty stem.

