## Secondary Endpoints:

- Postoperative restoration of femoral offset and leg length
- Radiographic measurements of stability and fixation
- Overall Survivorship
- Harris Hip Score
- Complications

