#### **Models for Continuous Measures**

Comparisons of study groups with regard to continuous baseline and secondary outcomes will be performed using standard statistical tests and will be chosen as appropriate for the scale and distribution of the measures being analyzed. For example, a t-test, Wilcoxon test, or one-way ANOVA (as appropriate) can be performed to assess differences.

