#### **Categorical Data Analyses**

Comparisons of study groups with regard to categorical baseline, secondary and safety outcomes will be performed using standard statistical tests and will be chosen as appropriate for the scale and distribution of the measures being analyzed.

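### Section 6.2 gives the leg-length and offset objective only between-arm tests, which cannot show whether the Taperloc Complete system reconstructs accurately

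*Combined protocol and SAP*

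**What the plan says.** All references are to the combined protocol and SAP.

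- **Objective.** Section 1.4 has five objectives. Three are worded as comparisons of the two stems. This one is not: "Determine whether the geometry and options available with the Taperloc Complete hip system can accurately reconstruct leg length and offset in this patient population". The Study Summary gives the reason for measuring leg length and offset: "to determine the suitability of the implant size range and neck geometry".
- **Arms.** Section 2.2: "The first group will receive a Taperloc Complete Reduced Distal standard length stem, and the second group will receive a Taperloc Complete Reduced Distal Microplasty". Both groups therefore receive the system that the objective asks about.
- **Endpoint.** Section 2.5 lists, as secondary, "Postoperative restoration of femoral offset and leg length". It names no reference measurement, tolerance or visit.
- **Analysis.** Section 6.2, on continuous measures: "Comparisons of study groups with regard to continuous baseline and secondary outcomes will be performed using standard statistical tests". On categorical data: "Comparisons of study groups with regard to categorical baseline, secondary and safety outcomes will be performed using standard statistical tests". The exploratory part of 6.2 is confined to bone density: "Repeated measures ANOVA models will be developed for each of the Gruen Zones".
- **Data.** The schedule in section 2.6.1 has standard radiographs pre-operatively, at 6 weeks, and at 1, 2 and 5 years.

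**The concern.** The objective asks how close the operated hips come to a target. The analysis asks whether two groups of operated hips differ from each other. These are different questions, and the second can come out null whether both stems restore the anatomy well or both miss by the same amount.

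Followed literally, the plan delivers an unadjusted p-value for the arm difference and no estimate of accuracy for a listed main objective. Two things are at stake. A finding of no difference in leg length or offset could be reported as evidence that the size range and geometry suit this population, even if every hip carried the same systematic error. And because nothing fixes what counts as accurate, that definition could be chosen after the data are seen.

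**Working it through.** The plan states no SD, tolerance, precision or sample size for this endpoint, so there is no figure of its own to reproduce. The calculation in section 6.1 concerns thigh pain and does not bear on this point.

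**Inputs from the document:** 100 hips in 100 patients (section 2.3), 50 per arm (Study Summary), and a test level of 0.05 without adjustment for secondary outcomes (section 6.2).

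**Assumed inputs:** SD of reconstruction error 3 to 8 mm, with 5 mm as the working value (6 mm in the simulation); common errors of 5, 8 and 10 mm as illustrations; all 100 hips evaluable unless stated.

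**Step 1: what each analysis estimates.** Write the mean error (post-operative value minus reference) as b + d1 in one arm and b + d2 in the other, where b is common to both.

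- Arm difference: (b + d1) − (b + d2) = d1 − d2. The common error b is gone, whatever its size.
- Pooled mean with equal arms: b + (d1 + d2)/2. The common error is retained.

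For example, if both arms lengthen the leg by an assumed 8 mm, the arm difference is 8 − 8 = 0 mm, while the mean error is 8 mm.

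**Step 2: simulation.** Two-sample t-test, 50 per arm, SD 6 mm, the same error in both arms, 20,000 runs. For comparison, a one-sample test of zero error on the same 100 hips.

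| Common error | Arm test rejects | One-sample test rejects |
|---|---|---|
| 0 mm | 5.1% | 5.1% |
| 5 mm | 5.4% | 100% |
| 10 mm | 5.0% | 100% |

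By step 1 the arm test's rejection rate cannot depend on the common error, so the spread in the middle column is simulation error.

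**Step 3: precision of a direct estimate (95% half-width).**

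- Pooled, n = 100: 1.96 × SD / √100
- Per arm, n = 50: 1.96 × SD / √50
- Arm difference, 50 against 50: 1.96 × SD × √(2/50)

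| SD | Pooled | Per arm | Arm difference |
|---|---|---|---|
| 3 mm | 0.59 | 0.83 | 1.18 |
| 5 mm | 0.98 | 1.39 | 1.96 |
| 8 mm | 1.57 | 2.22 | 3.14 |

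At SD 5 mm, the 8 mm example would be reported as 8 ± 0.98, or about 7.0 to 9.0 mm. With 80 evaluable hips the pooled half-width is 1.96 × 5 / √80 = 1.10 mm.

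**Step 4: proportion within tolerance.** The exact (Clopper-Pearson) 95% interval is 82.4% to 95.1% if 90 of 100 hips fall within tolerance, and 70.8% to 87.3% if 80 do.

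**The case against.** **The test wording is flexible.** Section 6.2 offers its tests as examples, to be chosen as appropriate. That leaves the choice of test open, but not the question: both relevant paragraphs are about comparing the groups.

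**Arm means would probably be tabulated anyway.** They might be, and a reader could then judge accuracy from them. But the plan does not commit to this, and a mean without a stated reference or tolerance does not settle whether reconstruction was accurate.

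**The arm comparison is legitimate.** This stands. The stems differ by 35 mm in length (section 1.2), and the documents do not establish that length has no effect on the leg length or offset achieved. The comparison should stay; it simply answers another question.

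**The numbers are illustrative.** This also stands. The documents give no SD and no typical error. The cancellation in step 1 needs neither; only the half-widths do.

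**Stronger readings that the documents do not support.** A reader might infer that the trial cannot answer the objective at all, since section 1.1 states that "The newer Taperloc Complete system (both Microplasty and standard length) has a neck angle of 133" degrees and no arm has the older angle. That does not follow. An absolute question needs a reference and a tolerance, not an arm with another neck, and sharing the geometry makes pooling natural. All 100 hips receive the system, and films are scheduled before and after surgery. A reader might also expect a conclusion on 133 against 138 degrees. Section 1.1 raises the criticism of the older angle but does not connect it to leg length or offset, and no objective in section 1.4 asks for that comparison, so no disclaimer is needed.

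**Conclusion.** The concern holds as a mismatch between objective and analysis. The only analyses that reach this endpoint are between-group tests, an error common to both arms cancels in them, and a non-significant result is uninformative about accuracy. The design and the scheduled films can support an answer; what is missing is a matching analysis with its reference, visit and tolerance.

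On the assumed SD of 5 mm and 100 evaluable hips, a direct estimate would fix the pooled mean error to within about 1.0 mm (0.6 to 1.6 mm for SD 3 to 8 mm). Fewer usable hips would widen this. The cancellation itself rests on no numerical assumption.

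The change is worth making, but its weight is limited: the endpoint is secondary, and neither primary endpoint nor the sample size is affected. The case report forms (Appendix 2) are not among the pages available, so what they record as a reference could not be checked.

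**What to change.** In section 6.2, add a paragraph for this endpoint that:

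- defines reconstruction error, separately for leg length and for offset, as the post-operative value minus a reference fixed before analysis, such as the contralateral side on the scheduled pre-operative radiograph where it is usable;
- names one post-operative visit, from those at which radiographs are already scheduled, for the main estimate;
- reports mean signed error and mean absolute error with 95% confidence intervals, pooled and per arm. The absolute error is needed because over- and under-correction offset each other in a signed mean; the per-arm results are needed because opposite errors in the two arms would offset each other in a pooled one;
- reports the proportion of hips within a tolerance that the investigators set before analysis, with an exact 95% interval;
- keeps the between-arm comparison as supportive, and states that a non-significant difference is not evidence of accurate reconstruction;
- counts and reports, by arm, the hips without a usable reference.

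A pre-operative templated plan should serve as a fallback reference only if the case report form records it; it is not in the schedule in section 2.6.1.

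The cost is a paragraph of text and some extra analysis, with no added patients or visits. The one real downside is that hips without a usable reference drop out of the estimate.
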